4 ANALYSIS SETS

Randomized Analysis Set

The Randomized Analysis Set will consist of all subjects who were randomized.

Subjects will be classified according to the randomized treatment assignment.

Safety Analysis Set

The Safety Analysis Set will consist of a subset of subjects in the Randomized Analysis Set who received at least one dose of study drug.

Subjects will be classified according to the actual treatment received.

Full Analysis Set

The Full Analysis Set will consist of a subset of subjects in the Safety Analysis Set who have both a Baseline value and at least 1 post-Baseline value for the CMAI total score.

Subjects will be classified according to the randomized treatment assignment.

Per-protocol Analysis Set

The Per-protocol Analysis Set will consist of a subset of subjects in the Full Analysis Set who do not have any protocol deviation which is considered to have substantial impact on the primary efficacy outcome, change from Baseline to Week 12 in the CMAI total score. The precise reasons for excluding subjects from the Per-protocol Analysis Set will be fully defined and documented *a priori* before the clinical database lock.

Subjects will be classified according to the randomized treatment assignment.

Pharmacokinetics Analysis Set

The Pharmacokinetics Analysis Set will consist of subjects with at least one measurable pimavanserin plasma concentration.

Subjects will be classified according to the actual treatment received.

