5.2.3 Alzheimer's Disease Cooperative Study – Activities of Daily Living Inventory (ADCS-ADL)

The ADCS-ADL is assessed at Baseline and Week 12/ET visits.

The ADCS-ADL is an inventory to assess activities of daily living (ADL) in subjects with AD. This is a caregiver-rated 23-item questionnaire, with sub-questions and sub-items for some items, including both basic (e.g. personal hygiene, eating, bathing) and instrumental (e.g. preparing a meal, using a telephone) ADLs. The recall period for this questionnaire is 4 weeks. The total score can range from 0 to 78, with lower scores indicating worse functioning.

A response of “DON’T KNOW” is not considered a missing value, rather it will be scored similarly to a “NO” response (i.e., that item score will be set to 0). The following table includes the item score range and the scoring rule. These rules will only apply in the analysis dataset; the raw data values will remain unchanged.

Table 2 ADCS-ADL Item Score Range

Item Number	Score Range	Note*
1-5, 8-12, 14, 17-19, 21, 22	0-3	For item 8, the score is sum of 8A, 8B, and 8C. The sub-question will be equal to 0 if the main or sub-question checks NO or DON’T KNOW. For item 18, the score is sum of 18A, 18B, and 18C. The sub-question will be equal to 0 if 1) the main or sub-question checks NO or DON’T KNOW; or 2) “patient is institutionalized” box is checked. For item 22, if NO or DON’T KNOW is checked then assign item score = 0. If YES is checked and one or more sub-item is checked, but the sub-question is not answered, then assign item score = 1. Otherwise, item score is equal to the non-missing sub-question score.
6	0-7	Sum of 6A (0-3; 0 if the main question checks NO or DON’T KNOW) and 6B (0-4).
7	0-5	
13, 15, 16, 23	0-4	For item 16, the score is sum of 16A (0-3; 0 if the main question checks NO or DON’T KNOW) and 16B (0-1; 0 if the main or sub-question checks NO or DON’T KNOW). For item 23, if NO or DON’T KNOW is checked then assign item score = 0. If YES is checked and one or more sub-item is checked, but the sub-question is not answered, then assign item score = 1. Otherwise, item score is equal to the non-missing sub-question score.
20	0-2	

* Item 7-21. If NO or DON’T KNOW is checked, then assign item score = 0. If YES is checked, the score of the item is sum of non-missing score(s) of the sub-question(s).

In addition to the total score, the following subscale scores will be defined:

- Basic subscale score: 6 Items (minimum = 0, maximum = 22)

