5.2.4 Neuropsychiatric Inventory – Clinician Rating Scale (NPI-C)

The complete NPI-C, which include agitation and aggression domains, will be administered at Baseline and Weeks 12/ET visits while only the NPI-C agitation and aggression domains will be administered at all other visits, i.e. Screening, and Weeks 2, 4, and 8 visits.

The NPI-C is a scale to assess the 14 neuropsychiatric symptoms (domains) in patients with dementia. For each domain, there are three NPI-C sections: caregiver interview, patient interview and clinician rating. The caregiver interview includes the frequency (0-4), severity (0-3) and distress (0-5) scores. The subject interview consists of the subject-reported frequency score (0-4). The clinician rating is a clinical impression severity score (0-3) based on all available interview information. For the caregiver interview, if a response of 0 is selected for the frequency score, then the severity and distress scores will be set to 0. For each domain, the domain score is the sum of the clinical impression severity scores within each domain, with higher scores denoting more serious symptoms. Before deriving any combined domain scores, if there are any missing items, the individual domain score will be imputed as follows:

For the delusions, hallucinations, aggression, elation/euphoria, aberrant motor disturbance, sleep disorders, appetite and eating disorders, and aberrant vocalizations domains, if only

1 item is missing then the respective domain score will be imputed by replacing the missing item with the mean of the non-missing items (rounded to the nearest integer) for that subject and timepoint within the domain. If more than 1 item is missing then the respective domain score will be missing.

For the agitation, dysphoria, anxiety, apathy/indifference, and irritability/lability domains, if up to 2 items are missing then the respective domain score will be imputed by replacing each missing item with the mean of the non-missing items (rounded to the nearest integer) for that subject and timepoint within the domain. If more than 2 items are missing then the respective domain score will be missing.

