For the disinhibition domain, if up to 3 items are missing then the respective domain score will be imputed by replacing each missing item with the mean of the non-missing values (rounded to the nearest integer) for that subject and timepoint within the domain. If more than 3 items are missing then the respective domain score will be missing.

Table 3 NPI-C Domain Score

NPI-C Domain	# items	Domain Score Range	Maximum Missing Items Allowed for Deriving the Domain Score*
Delusions	8	0 – 24	1
Hallucinations	7	0 – 21	1
Agitation	13	0 – 39	2
Aggression	8	0 – 24	1
Dysphoria	13	0 – 39	2
Anxiety	14	0 – 42	2
Elation/Euphoria	6	0 – 18	1
Apathy/Indifference	11	0 – 33	2
Disinhibition	16	0 – 48	3
Irritability/Lability	12	0 – 36	2
Aberrant Motor Disturbance	9	0 – 27	1
Sleep Disorders	8	0 – 24	1
Appetite and Eating Disorders	9	0 – 27	1
Aberrant Vocalizations	8	0 – 24	1

* For each domain, the maximum number of missing items allowed for deriving the domain score is the nearest integer to but $\leq 20\%$ of the total items in that domain. If there are any missing items, the individual domain score will be imputed first before calculating the combined domain scores.

The NPI-C combined agitation and aggression domain score is calculated as the sum of the agitation domain score and the aggression domain score. If either the agitation or aggression domain score is missing, the NPI-C combined agitation and aggression domain score will be missing.

The NPI-C combined delusions and hallucinations domain score is calculated as the sum of the delusions domain score and the hallucinations domain score. If either the delusions or hallucinations domain score is missing, the NPI-C combined delusions and hallucinations domain score will be missing.

The NPI-C combined dysphoria and apathy/indifference domain score is calculated as the sum of the dysphoria domain score and the apathy/indifference domain score. If either the dysphoria or apathy/indifference domain score is missing, the NPI-C combined dysphoria and apathy/indifference domain score will be missing.

The NPI-C total score is calculated as the sum of all 14 individual domain scores. The NPI-C total score ranges from 0 to 426, with higher scores denoting more serious symptoms. After applying the preceding data handling rules, if any of the domain scores remain missing, the total score will be missing.

5.2.5 Modified Alzheimer's Disease Cooperative Study – Clinical Global Impression-Change (mADCS-CGIC)

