12.3 Handling of Missing Data

The primary efficacy variable will be summarized assuming missing at random using an MMRM method. Total scores that are missing, after any imputation of individual missing items as described in [Section 5.2.1](#), will not be imputed.

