The change from Baseline to Week 12 in the ADCS-ADL and NPI-C total score, combined delusions and hallucinations, combined dysphoria and apathy/indifference and individual domain scores (except the agitation and aggression domains) will be summarized using an analysis of covariance (ANCOVA) model with effects for treatment group (pimavanserin 34 mg, pimavanserin 20 mg, or placebo) and geographic region (North America, Europe, or Rest of World) as factors, and the Baseline value of the endpoint being summarized as a covariate. Missing values will be imputed with the previous value (including Baseline) for

that subject, i.e. last observation carried forward (LOCF). In addition, an observed-case summary, ignoring missing values, will also be presented.

At Week 12, the effect size (Cohen's d) for the change from Baseline between the treatment groups (each pimavanserin group versus placebo group) will be calculated using the following formula:

$$\text{Effect size} = \frac{\text{LS mean difference}}{\sqrt{\text{MSE}}}$$

Where MSE is the mean squared error from the ANCOVA model. The sign (+ or -) of the effect size will be chosen so that an effect size favoring pimavanserin will be reported as a positive number and an effect size favoring placebo will be reported as a negative number.

The change from Baseline to each post-Baseline timepoint (Weeks 4, 8 and 12) in the MMSE will be summarized using an MMRM model in Full Analysis Set similar to that described above for the primary endpoint in [Section 13.1](#), except that the Baseline value of the MMSE will be included in the model instead of the Baseline CMAI total score. Also, the MMSE is not measured at Week 2.

Results will be presented in summary table similar to the outputs described in Section 13.1.

The use of rescue medication is determined from the Rescue Medications eCRF. The proportion of subjects taking any rescue medication during the treatment period for the Full Analysis Set will be summarized by treatment group.

Correlations among efficacy endpoints (observed cases) at Baseline (combining all 3 treatment groups) and for change from Baseline at Week 12 (combining all 3 treatment groups and by treatment group) will be assessed using Spearman's rank correlation coefficient (Spearman's rho) and presented in a correlation matrix. The 95% CIs for the Spearman's rank correlation coefficients will also be presented.

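### Should SAP 13.3 stop carrying Baseline forward to Week 12 on the ADCS-ADL and NPI-C ANCOVA endpoints and let observed cases lead?

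*SAP*

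**What the plan says.** SAP 13.3 analyses the Week 12 change in ADCS-ADL, NPI-C total, the two combined scores (delusions with hallucinations, dysphoria with apathy/indifference) and the individual NPI-C domains other than agitation and aggression by ANCOVA on treatment, region and Baseline. For missing values it says: "Missing values will be imputed with the previous value (including Baseline) for" that subject, and it calls this LOCF. It then adds: "In addition, an observed-case summary, ignoring missing values, will also be presented". Cohen's d divides the LS mean difference by the root of the MSE: "Where MSE is the mean squared error from the ANCOVA model".

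Four other places matter.

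- Schedule: "The ADCS-ADL is assessed at Baseline and Week 12/ET visits" (SAP 5.2.3) and "The complete NPI-C, which include agitation and aggression domains, will be administered at Baseline and Weeks 12/ET visits" (SAP 5.2.4). Only the agitation and aggression domains are also rated at Weeks 2, 4 and 8.
- Population: the Full Analysis Set takes treated subjects "who have both a Baseline value and at least 1 post-Baseline value for the CMAI total score" (SAP 4). It does not require a later NPI-C or ADCS-ADL.
- NPI-C total: "After applying the preceding data handling rules, if any of the domain scores remain missing, the total score will be missing" (SAP 5.2.4).
- Primary endpoint: "The primary efficacy variable will be summarized assuming missing at random using an MMRM method" (SAP 12.3). That section covers the primary variable only.

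**The concern.** A subject can enter the Full Analysis Set on a Week 2 CMAI and then leave without an early-termination visit. With no scheduled visit between Baseline and Week 12 for these scales, the previous value is Baseline itself, and the change is exactly zero on up to 16 endpoints. A completer can be caught too: if one NPI-C domain stays missing after item imputation, the Week 12 total is missing and the Baseline total takes its place.

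If the arms change on average, such zeros pull a true difference and its Cohen's d towards zero. If missingness differs between arms, they can create a difference where there is none. The assumption also differs from the missing-at-random one used for the primary endpoint. And if the report can choose which of two fits to feature and which supplies Cohen's d, that choice could follow the data.

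**Working it through.** **Count of endpoints.** SAP Table 3 lists 14 domains with 142 items. At 0 to 3 points each, 142 × 3 = 426, which matches the NPI-C maximum stated in SAP 5.2.4. ANCOVA endpoints: 1 (ADCS-ADL) + 1 (NPI-C total) + 2 (combined) + (14 − 2) domains = 16.

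**Inputs.** From the documents: 111 randomized 1:1:1, so 37 per arm, and a Week 12 window of Days 71 to 99 (SAP Table 4). The documents give no missing rate, mean change or SD for these scales. Assumed, in SD units with improvement positive: dropout 10 to 20%, early-termination capture 50 to 80%, placebo change m = 0.5, true difference δ = 0.50 or 0.

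**Share set to zero change.** p = dropout × (1 − capture). Range: 0.10 × 0.2 = 0.02 to 0.20 × 0.5 = 0.10, or 0.7 to 3.7 subjects per arm.

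**Precision.** SE = √(2/37) = 0.232; 95% half-width = 1.96 × 0.232 = 0.46.

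**Expected LOCF difference** = (1 − p₃₄)(m + δ) − (1 − p_pbo)m.

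| Zero-change share, placebo / 34 mg | True δ | LOCF estimate | LOCF coverage |
|---|---|---|---|
| 2% / 2% | 0.50 | 0.98 × 0.50 = 0.49 | 95.4% |
| 5% / 5% | 0.50 | 0.95 × 0.50 = 0.475 | 94.8% |
| 10% / 10% | 0.50 | 0.90 × 0.50 = 0.45 | 94.2% |
| 4% / 10% | 0.50 | 0.90 × 1.0 − 0.96 × 0.5 = 0.42 | 93.2% |
| 10% / 20% | 0.50 | 0.80 × 1.0 − 0.90 × 0.5 = 0.35 | 90% |

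Coverage is from 4000 simulated trials of 3 × 37, with ANCOVA on treatment, region (assumed split 40/40/20%) and Baseline (assumed correlation 0.3 with improvement). The last row lies outside the 2 to 10% range derived above.

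With no drug effect, the shift is (p₃₄ − p_pbo)m. At 4% vs 10% its size is 0.06 × 0.5 = 0.03, or 0.03/0.232 = 0.13 SE. With a mean change of 1 it is 0.06, or 0.26 SE.

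**Cohen's d.** The ratio of LOCF d to observed-case d is (1 − p)/√(MSE_LOCF/0.91), where MSE_LOCF = (1 − p) + p(1 − p) × mean(m²) − 0.09(1 − p)². Here mean(m²) averages the squared mean changes of the three arms: 0.75 if 20 mg works as well as 34 mg, 0.50 if it has no benefit. At p = 2, 5 and 10% the ratio is 0.98, 0.95 to 0.96, and 0.91 to 0.92.

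**Would an observed-case lead be better?** Not uniformly. Let poorer responders be missing more often (latent correlation 0.5), with no drug effect:

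| Missing share, placebo / 34 mg | Observed-case bias | LOCF bias |
|---|---|---|
| 4% / 10% | +0.05 | +0.01 |
| 10% / 20% | +0.08 | +0.01 |

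With a true 0.50 at 4% vs 10%, observed cases give 0.55 and LOCF 0.46, so the errors are similar in size and opposite in sign. When missingness is ignorable, observed cases do better: coverage at 4% vs 10% is 94.6% against 93.2%.

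**What an observed-case lead would drop.** Under the same assumptions, 0.10 × 0.5 = 5% to 0.20 × 0.8 = 16% of subjects leave with a real early-termination value. LOCF uses these values; an observed-case Week 12 analysis drops those taken before Day 71. If all were that early, observed-case missingness would equal the full 10 to 20% dropout. Sample loss alone would then widen intervals by a factor of 1/√0.9 = 1.05 to 1/√0.8 = 1.12. The simulations above contain no such group, so they leave out the setting in which LOCF draws on real data.

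**The case for a change.** The best case for acting is cost. One sentence written before unblinding would fix which result leads and which fit gives Cohen's d, and a small table would show how many Week 12 values are copies of Baseline. The MMRM endpoints use observed cases, so these 16 rest on a different assumption that the SAP does not justify.

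The mechanism stands in full for a subject with no later value. For the NPI-C total it also assumes that LOCF acts on the total score. SAP 5.2.4 supports that reading, but if agitation and aggression were carried from Weeks 2 to 8 by domain, the total need not show zero change. The completer route is narrow, since item imputation and ADCS-ADL prorating (SAP 5.2.3 and 5.2.4) act first. It affects only the total and any combined score that contains the missing domain; the other domains keep their Week 12 values.

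The rest is weaker. The LOCF sentence follows directly on the ANCOVA specification, the observed-case result is introduced as an addition, and the SAP speaks of a single ANCOVA model. An analyst would take LOCF as leading and take d from that fit. SAP 1 leaves table specifications to a separate document, where a label or footnote belongs. SAP 5 has all data listed, so subjects without a later value can be identified. A count table would change no estimate. The contrast with the primary endpoint carries little weight: CMAI has four post-Baseline visits, whereas these scales have one, so the same repeated-measures model is not available.

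**Conclusion.** No change follows. The zero-change effect is real and openly stated in SAP 13.3, but it touches exploratory endpoints with no hypothesis testing (SAP 12 and 12.4). The observed-case result is shown beside it, and sites are asked to make every effort to complete the early-termination visit (Protocol 4.2), which collects these scales (Protocol 3.2.6).

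At an assumed 2 to 10% zero change in each arm, attenuation of a 0.50 SD difference is 0.01 to 0.05 SD. Unequal shares of 4% and 10% take it to 0.42. Both are small against a half-width of 0.46. Only with 20% of an arm lacking any later value does coverage fall to about 90%. The missing rates, mean changes and correlations are all assumptions; the direction of the effect depends on whether arms improve or worsen on average.

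Making observed cases the lead would be a trade-off rather than an improvement: it gains when missingness is ignorable, loses when poorer responders leave and there is no drug effect, and discards real measurements before Day 71. The unnamed source of Cohen's d is a gap that analysts fill sensibly from the order of the text.

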13.4 Responder Analyses

In the responder analyses, since CMAI is an interval scale that lacks a natural zero point (1 = Never), the percent change in CMAI total score will be calculated based on corrected scores after subtracting 29 points from the raw scores. For example, if a subject's Baseline CMAI total score is 79 and Week 12 CMAI total score is 29 (absent of all agitation behaviors), the percent change from Baseline to Week 12 in CMAI total score will be calculated as $[(29 - 29) - (79 - 29)] \div (79 - 29) \times 100\% = -100\%$.

Multiple types of responders will be summarized within each treatment group at each post-Baseline visit:

- $\geq 20\%$, $\geq 30\%$, $\geq 50\%$, $\geq 75\%$ and 100% reduction in the CMAI total score from Baseline
- $\geq 20\%$, $\geq 30\%$, $\geq 50\%$, $\geq 75\%$ and 100% reduction in NPI-C combined agitation and aggression domain scores from Baseline
- $\geq 20\%$, $\geq 30\%$, $\geq 50\%$, $\geq 75\%$ and 100% reduction in the individual agitation and aggression NPI-C domain scores from Baseline
- mADCS-CGIC score of 1 (marked improvement) or 2 (moderate improvement)

Other responder criteria based on point changes may be included based on examination of cumulative distribution functions and anchoring to the ADCS-CGIC.

For each of these responder analyses, the proportion of responders will be summarized by treatment group at each timepoint using observed cases and also with missing values imputed as non-response. The adjusted difference in percent responders between the treatment groups (pimavanserin group minus placebo group) using the weighting scheme of Cochran-Mantel-Haenszel and Newcombe's 95% CI stratified by geographic region will be presented. In addition, percent responders by treatment group at Week 12 will also be presented in bar charts.

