Pharmacokinetic Assessments and Endpoints	
Blood samples of pimavanserin will be collected at Baseline (pre-dose), Weeks 2, 4, and 12 (end of study [EOS]/ET). (Note: If collection at Week 2 does not occur, then collection should be attempted at Week 8.) When possible, blood samples of pimavanserin will be collected from subjects who experience an SAE or an AE leading to discontinuation.
 
For all PK samples (scheduled and unscheduled), the dates and times of administration of the last 3 doses of study drug should be recorded. For samples collected from subjects who experience an SAE or an AE leading to discontinuation, the date and time of the last dose prior to the SAE or AE should also be recorded.
 
Plasma concentration data will not be analyzed until the official unblinding of the clinical database at the end of the study.
 
Pharmacokinetic Endpoint:
 

• Plasma concentration of pimavanserin and AC-279

Statistical Methods	
The Full Analysis Set includes all randomized subjects who received at least 1 dose of blinded study drug and who have both a baseline value and at least 1 post-baseline value for the CMAI total score. The Full Analysis Set will be used for the summary of all efficacy endpoints.
 
The Per-protocol (PP) Analysis Set will be defined prior to unblinding the study for the final summaries. Subjects will be summarized based on their randomized treatment assignment.
 
Safety summaries will be conducted using the Safety Analysis Set,

which is defined as all subjects who received at least 1 dose of blinded study drug.

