## **9.3 Handling of Dropouts and Missing Data**

Handling of missing values will be described in detail in the SAP. For the responder analyses, two sets of analyses will be provided, one based on observed cases and the other counting subjects with missing values as non-responders.

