## **9.5 Study Subjects**

### **9.5.1 Analysis Sets**

The Safety Analysis Set includes all randomized subjects who received at least 1 dose of study drug (pimavanserin or placebo). Subjects will be summarized based on the treatment which they actually received. The Safety Analysis Set will be used for all safety analyses.

The Full Analysis Set includes all randomized subjects who received at least 1 dose of study drug and who have both a baseline value and at least 1 post-baseline value for the CMAI total score. Subjects will be summarized based on their randomized treatment. The Full Analysis Set will be used for the summaries of all efficacy endpoints. The Per-protocol (PP) Analysis Set will be defined prior to unblinding the study for the final summaries. Subjects will be summarized based on their randomized treatment.

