5.2.1 Cohen-Mansfield Agitation Inventory Long-form (CMAI)

The CMAI is assessed at Baseline, and Weeks 2, 4, 8 and 12/ET visits.

The CMAI is a 29-item scale designed to systematically assess agitation, rated on a 7-point (1-7) scale of frequency (1 = Never; 2 = Less than once a week; 3 = Once or twice a week; 4 = Several times a week; 5 = Once or twice a day; 6 = Several times a day; 7 = Several times an hour). Subjects are rated by their primary caregiver regarding the frequency with which they manifest physically aggressive, physically non-aggressive, and verbally agitated behaviors. The CMAI in this study is to be completed by interview of the caregiver. Ratings are inclusive of the 2 weeks prior to the administration of the scale.

In addition to the 7-point frequency scale, there are two other options for rating the behavior: 1) “8 - would occur if not prevented” (e.g., a person is physically restrained so he/she cannot pace), and 2) “9 - not applicable” (e.g., a non-verbal resident not being able to repeat sentences or questions, or a person who cannot walk or move a wheelchair not being able to pace, an amputated person not being able to kick). These two ratings are used only if the behavior really has never occurred in the past two weeks. If it has occurred, then the 1-7 point frequency scale should be used. These ratings of 8 and 9 are not included in the CMAI total score calculation. The CMAI has a range of 29-203 points, with higher scores indicating more severe agitation symptoms. If there are less than 6 missing items then the total score will be imputed by replacing each missing item with the mean (rounded to the nearest integer) of the non-missing values for that subject and timepoint. If there are more than 5 missing items then the total score will be missing.

In addition to the total score, behavioral subscales will be defined as follows ([Rabinowitz et al, 2005](#)):

- Aggressive Behavior: 12 Items (minimum = 12, maximum = 84)
- Sum of scores from items 3, 4, 7, 8, 9, 10, 11, 13, 14, 15, 21 and 25
- Physically Non-aggressive Behavior: 6 Items (minimum = 6, maximum = 42)
- Sum of scores from items 1, 2, 16, 22, 26, and 29
- Verbally Agitated Behavior: 4 Items (minimum = 4, maximum = 28)
Sum of scores from items 5, 6, 18, and 19
- Hiding and Hoarding : 2 Items (minimum = 2, maximum =14)
Sum of score from items 23 and 24

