5.3.1 Unscheduled Assessments

Both scheduled and unscheduled assessments, including early termination visits, will be considered for planned timepoint summaries. All assessments will be presented in data listings.

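### Dosed subjects with no usable post-Baseline CMAI total drop out of the missing-as-non-response responder analysis instead of counting as non-responders

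*SAP*

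**What the plan says.** SAP 13.4 defines responders by percent reduction on the CMAI total and the NPI-C agitation and aggression scores, and by a mADCS-CGIC rating of 1 or 2. Each proportion is to be reported by arm and visit "using observed cases and also with missing values imputed as non-response", with a region-stratified difference from placebo and a Newcombe 95% interval. Protocol 9.3 describes the two versions as one on observed cases and "the other counting subjects with missing values as non-responders".

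SAP 13.4 does not say which subjects form the denominator. The protocol does so in general terms. Section 9.5.1 states: "The Full Analysis Set will be used for the summaries of all efficacy endpoints". The synopsis has the same rule: "The Full Analysis Set will be used for the summary of all efficacy endpoints". SAP 19 lists no changes to the protocol's analyses.

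SAP 4 builds the Full Analysis Set from dosed subjects "who have both a Baseline value and at least 1 post-Baseline value for the CMAI total score". SAP 4 also defines a wider set: "The Randomized Analysis Set will consist of all subjects who were randomized". No responder analysis is assigned to that set or to the Safety Analysis Set.

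**The concern.** Counting missing values as non-response is meant to make loss of data count against the arm in which it occurs. A dosed subject with no post-Baseline CMAI total is missing at every visit, so the rule settles that subject's CMAI responder status without any post-Baseline score. The Full Analysis Set removes the subject before the rule can act.

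The post-Baseline requirement suits the repeated-measures model and the observed-case proportions, which cannot use such a subject. It has no function in the version where missing means failure.

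The requirement also reaches the other scales. A subject with a post-Baseline mADCS-CGIC or NPI-C rating but no scorable CMAI total is left out of those responder analyses too. SAP 5.2.1 shows how this can happen without dropout: "If there are more than 5 missing items then the total score will be missing".

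At stake are the Week 12 proportions, bar charts, adjusted differences and intervals, in a table whose label says that missing subjects were counted as failures.

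**Working it through.** The plan states no figure to reproduce: it gives no expected dropout, responder rate or power. The check has two parts, the definitions and then the arithmetic.

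**Definitions**

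1. Responder rule: missing counts as non-response (SAP 13.4, protocol 9.3).
2. Set: Full Analysis Set for all efficacy endpoints (protocol 9.5.1 and synopsis), unchanged by SAP 19.
3. Entry to the set: at least one dose, a Baseline CMAI total and at least one post-Baseline CMAI total (SAP 4).
4. It follows that a dosed subject with a Baseline CMAI but no post-Baseline total is a failure under step 1 and is absent under step 3.

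**Inputs**

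- 111 randomized (SAP 3.5), allocated 1:1:1 (SAP 3.3), so n = 111/3 = 37 per arm. I assume that arms are equal, that all were dosed and that all have a Baseline value.
- k = subjects in an arm with no usable post-Baseline CMAI total. The documents give no count, so k is an assumption.
- r = responders in the arm, or the rate among those retained. Also assumptions.

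**One arm, 50% rate among those retained**

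The rate with all n in the denominator is 0.5 × (37 − k)/37, so the inflation is 0.5 − 0.5 × (37 − k)/37 = 0.5 × k/37.

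- k = 1: 1.4 points
- k = 2: 2.7 points
- k = 3: 4.1 points (50% reported, 45.9% with all 37 counted)

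**One arm, fixed number of responders: r/(37 − k) against r/37**

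| r | all 37 | k = 1 | k = 3 | k = 5 |
|---|---|---|---|---|
| 11 | 29.7% | 30.6% | 32.4% | 34.4% |
| 15 | 40.5% | 41.7% | 44.1% | 46.9% |
| 19 | 51.4% | 52.8% | 55.9% | 59.4% |

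For the CMAI, an arm's rate can only rise (or stay at zero), because everyone removed is a failure under the rule. That is not guaranteed for mADCS-CGIC or NPI-C, where a removed subject may have a rating on that scale and may be a responder.

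**Difference between arms (crude, unstratified), 15 active and 11 placebo responders**

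With all 37 per arm: 15/37 − 11/37 = 10.8 points.

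- 4 active and 1 placebo removed: 15/33 − 11/36 = 14.9 points (shift +4.1)
- 3 and 3 removed: 15/34 − 11/34 = 11.8 points (shift +1.0)
- 1 active and 4 placebo removed: 15/36 − 11/33 = 8.3 points (shift −2.5)
- none removed: no shift

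**Against the precision available**

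At 37 per arm and rates near 50%, the approximate half-width of a 95% interval for a difference is 1.96 × √(2 × 0.25/37) = 23 points. A 4.1-point shift is under one fifth of that.

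**The case against.** **The set is inferred.** SAP 13.4 is silent, while SAP 13.1 to 13.3 name the Full Analysis Set for the CMAI, ZBI, MMSE and rescue medication. Responder status is also absent from the listed endpoints. This stands as a drafting point. Even so, the protocol's general rule and SAP 19 leave the Full Analysis Set as the natural reading, and no other set is offered for these analyses.

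**Most early leavers stay in.** A reader might infer that early dropouts as a group are excluded. The documents do not support that. Protocol 4.2 asks for every effort to complete the early-termination visit, protocol 3.2.6 includes the CMAI at that visit, and SAP 5.3.1 states: "Both scheduled and unscheduled assessments, including early termination visits, will be considered for planned timepoint summaries". The Week 2 window opens on Day 2, and up to 5 missing CMAI items are imputed. A subject who stops in the first week with a scorable termination CMAI remains in the set and counts as a non-responder at later visits without data. The point is confined to subjects with no usable post-Baseline total.

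**The direction is not fixed.** A reader might infer that the difference is biased toward pimavanserin. It is so only if the active arm loses more such subjects, or if losses are equal and its rate is already higher. Heavier placebo losses can reverse it, as shown above.

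**No decision depends on it, and exclusions are disclosed.** No hypothesis test is planned and the study is declared not powered for efficacy. SAP 6 gives set sizes by arm and lists each excluded subject with reasons. This holds, and it limits severity. A reader could rebuild crude CMAI rates from the listing, but not readily the region-stratified difference and interval.

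**Conclusion.** The point holds in a narrow form. Read with the protocol, SAP 13.4 removes dosed subjects with no usable post-Baseline CMAI total from an analysis in which protocol 9.3 would count them as failures, and it applies the same CMAI condition to the NPI-C and mADCS-CGIC responder analyses. The inflation of each arm's CMAI rate is one-directional, at about 1.4 points per subject under the 37-per-arm and 50% assumptions. The effect on the difference is not one-directional.

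The documents do not give the number affected. It is likely small, and if it is zero nothing changes. They offer no basis for saying that the trial's conclusions would alter: the shifts illustrated are small beside the expected interval width, and the analysis is descriptive. This is a cheap improvement of minor severity.

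**What to change.** Add to SAP 13.4 that the missing-as-non-response version uses all randomized subjects who took at least one dose, by randomized arm, with a Baseline value of the scale being analysed and no post-Baseline CMAI requirement. The Baseline condition is needed because percent reduction is undefined without it; mADCS-CGIC needs none. State in the same place that the observed-case version stays in the Full Analysis Set.

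The cost is one sentence, with no new data or model and no effect on the primary or secondary analysis. CMAI responder rates may be slightly lower, and the denominator will differ from the other efficacy tables, so the table should carry a footnote naming its set.
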